Study Title:**Reflectance Confocal Microscopy (RCM) to diagnose basal cell carcinoma: HS-MAV-003****Background**

Basal cell carcinoma (BCC) is the commonest skin cancer in the UK and its incidence is rising year on year. Extrapolation of data from the East Norfolk and Waveney area of the UK suggests approximately 200 000 patients had 247 000 BCCs treated surgically that in 2010 (this estimate does not include those treated by other means such as cryotherapy, topical chemotherapy, photodynamic therapy or radiotherapy, without histology) [1].

There are many treatments for BCC depending on the subtype. Thin or superficial BCCs (sBCC) can be treated with topical therapies such as 5-fluorouracil, photodynamic therapy or liquid nitrogen (cryotherapy). Thicker, deeper tumours require surgical excision or radiotherapy. Higher risk lesions, or those of the head and neck where there are significant morbidity risks, can be treated using mohs Micrographic Surgery where removal is histologically controlled.

Reflectance confocal microscopy (RCM) is a high resolution, non-invasive method for visualising skin in cellular detail in-vivo. In studies conducted overseas, confocal microscopy has been shown to be highly effective in the diagnosis of Basal Cell Carcinoma [2-5]. Reported sensitivity and specificity for RCM in diagnosing BCC range from 83-100% and 79-97% [6-12]

A 2004 study showed that the presence of two or more criteria is 100% sensitive for the diagnosis of BCC, and with 4 or more RCM criteria present the specificity was 95.7% and sensitivity was 82.9% [6].

A recent study examined the performance of both the wide field Vivascope 1500 and the narrow field Vivascope 3000. While the traditional wide probe RCM (WTP-RCM) provides more coverage of the lesional tissue, the smaller-diameter handheld RCM (HH-RCM) allows better access to limited anatomic locations [12]. Both instruments are available for this study, and either / both will be used depending on anatomic considerations.

Comparison between TWP-RCM vs. HH-RCM was as follows: sensitivity (100% vs. 93%), specificity (78% for both probes), positive predictive value (96% vs. 95%), and negative predictive value (100% vs. 70%) respectively [12]. Studies have also developed diagnostic criteria for BCC subtypes [11].

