1. Recurrent or other higher-risk BCC
2. Patient with basal cell naevus syndrome
3. Patient treated with hedgehog inhibitor medication (vismodegib)
4. Patient not suitable for diagnostic biopsy
5. Location of lesion unsuitable, inaccessible or impractical for scanning with RCM as determined by investigator

6. Patient with co-morbidities such as other skin disease

Informed Consent

The Investigator, or an authorised member of their team, will obtain written informed consent for patients. It is anticipated that patients will be approached regarding participation after diagnosis when they have been identified as having an equivocal lesion requiring biopsy under standard of care.

When obtaining informed consent, investigators must ensure that they adequately explain the aim, anticipated benefits and potential hazards of taking part in the trial to the patient. Investigators should also stress that patients are free to refuse to take part or withdraw from the trial at any time. The patient should be given ample time (when possible, 48 hours) to read the appropriate patient information sheet and to discuss their participation with others if requested. The patient must be given an opportunity to ask questions which should be answered to their satisfaction. The right of the patient to refuse to participate in the trial without giving a reason must be respected.

Patients, who agree to take part, should be asked to sign and date the latest version of the consent form. The Investigator, or an authorised member of their team, must then sign and date the form. A copy of the form should be given to the patient, a copy should be filed in the clinic notes, and the original placed in the site file.

Study Intervention

Patients will be assessed in clinic by a consultant dermatologist. Patients with a non-pigmented lesion suspected to be BCC will be invited to participate. Clinical and dermoscopic images will be taken by the team as part of their routine standard of care. Patients will be invited to participate in the trial and provided with a patient information leaflet. They will be given sufficient time to review the information sheet and ask questions.

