The 95% confidence interval for the specificity and sensitivity will be calculated for both observers. For the confocal microscope to be concluded as having a specificity equal to that of the biopsy the lower limit of the 95% confidence interval must not be less than 94%. Similarly for sensitivity the lower limit of the 95% confidence must not be less than 92%. To assess the inter-observer agreement the Kappa statistic will be reported alongside the proportion of agreements and disagreements.

Sample size calculation

For a specificity of 97% with a maximum marginal error of 3% for constructing the 95% confidence interval a sample size of 125 is required. For a sensitivity of 95% with a maximum marginal error of 3% for constructing the 95% confidence interval a sample size of 203 is required. A total sample size of 328 will be required to test both a specificity of 97% and sensitivity of 95% with a marginal error of 3% for both.

Data management and analysis

The Clinical Record Forms (CRFs) must be completed, signed and dated by the Investigator or an authorised member of staff prospectively. The completed originals will be collected by the trials co-ordinator and held in the site file as source documents. It is the responsibility of the Investigator to ensure that CRFs have been completed correctly and that the data are accurate. Entries should be made in ballpoint pen and should be legible. Any errors should be crossed out with a single stroke, the correction inserted and the change initialled and dated. All missing and ambiguous data will be queried. The CRF may be amended as appropriate; this will not constitute a protocol amendment. The revised CRF should be used by all participating sites with immediate effect.

The data will be transferred anonymously to a password -secured electronic database. All patients will be pseudo-anonymised. Data will be stored in databases in the Dermatology Department, Skin Care Network, and any copies to be taken off site (for example for statistical analysis or for analysis by the equipment provider) will be anonymised and will be protected by encryption and password. Access will be restricted to medical and research personnel, and appropriate support personnel. Specific trial information will be restricted to Investigators and collaborators. The trial co-ordinator will be responsible for the daily administration of the database.

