An initial interim analysis of the data will be planned after 25 patients to ensure the RCM images are of sufficient quality to continue and complete the study. Data validation will be co-ordinated under the supervision of the trial statistician once the recruitment target has been reached. The final analysis and publication of results will be undertaken after all patients have been recruited. The accrual period is estimated to be 12 months but will be continued until sufficient numbers are obtained for the study to reach significance. Once the dataset is complete, assessment of the RCM images by the blinded investigators will take place to allow statistical analysis of the primary and secondary endpoints, namely specificity, sensitivity and kappa statistics. Analysis of the final dataset is expected to take place within 6 months of completion of accrual. Publication is expected within 12 months of completing the trial.

Ethical Issues

The study proposal is subject to approval by the appropriate Ethics Committee, and will adhere to Good Clinical Practice Guidelines. The study will be conducted according to the principles of the Declaration of Helsinki and in accordance with the Medical research Involving Human Subjects Act (WMO).

Amendments

Amendments are changes made to the research after a favourable opinion by the accredited Ethics Committees has been given. All amendments will be notified to the Ethics Committees that gave a favourable opinion.

A 'substantial amendment' is defined as an amendment to the terms of the Ethics Committee(s) application, or to the protocol or any other supporting documentation, that is likely to affect to a significant degree:

- the safety or physical or mental integrity of the subjects of the trial;
- the scientific value of the trial;
- the conduct or management of the trial; or
- the quality or safety of any intervention used in the trial.

All substantial amendments will be notified to the Ethics Committees and to the competent authority.

Non-substantial amendments will not be notified to the accredited Ethics Committees and the competent authority, but will be recorded and filed by the sponsor.

Annual Progress Report

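### The total of 328 gives a 3% margin for both sensitivity and specificity only if about 62% of lesions prove to be BCC, and the plan never states that assumption

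*Combined protocol and SAP*

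**What the plan says.** Under 'Sample size calculation' the plan derives two numbers separately: "For a specificity of 97% with a maximum marginal error of 3% for constructing the 95% confidence interval a sample size of 125 is required", and "For a sensitivity of 95% with a maximum marginal error of 3% for constructing the 95% confidence interval a sample size of 203 is required". It adds them and concludes that "328 will be required to test both a specificity of 97% and sensitivity of 95% with a marginal error of 3% for both".

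The synopsis names histology as the comparator for both measures. Recruitment is a single prospective cohort; 'Study Intervention' says "Patients with a non-pigmented lesion suspected to be BCC will be invited to participate", and every participant is imaged and then biopsied. 'Informed Consent' says that patients are approached when "they have been identified as having an equivocal lesion requiring biopsy under standard of care".

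'Summary of statistical methods' requires the lower 95% limit to be at least 94% for specificity and at least 92% for sensitivity. It does not name the interval method.

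On accrual, 'Data management and analysis' says that recruitment "will be continued until sufficient numbers are obtained for the study to reach significance". No section gives an expected BCC prevalence, a quota by histology, or a required count of BCC or non-BCC lesions.

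**The concern.** The two measures have different denominators, and histology decides which one each lesion enters. A requirement of 203 for sensitivity means 203 BCC lesions, and 125 for specificity means 125 non-BCC lesions. Adding them gives a valid total only if patients arrive in that proportion. In an unselected cohort with suspected BCC, the proportion is whatever the clinic's case mix happens to be.

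If BCC is more common than the sum implies, specificity is estimated less precisely than claimed. If it is less common, sensitivity is. Sensitivity and specificity together are the primary endpoint, and each success limit is the planned value minus exactly 3 points (97% to 94%, 95% to 92%). On the plan's own formula, a half-width above 3% means that the criterion fails even when the planned value is observed.

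**Working it through.** **Inputs.** Planned specificity 0.97, planned sensitivity 0.95, margin 0.03, 95% confidence and total 328, all from 'Sample size calculation'. The two-sided z = 1.96 is inferred; it reproduces both stated figures.

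**Reproducing the plan.** n = z² p(1 − p) / d².

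- Specificity: 1.96² × 0.97 × 0.03 / 0.03² = 124.2, rounded up to 125.
- Sensitivity: 1.96² × 0.95 × 0.05 / 0.03² = 202.8, rounded up to 203.
- Sum: 125 + 203 = 328.

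**Implied case mix.** 203 / 328 = 61.9% BCC. The other possible reading, that every lesion counts towards both measures, would make the addition pointless, since 203 would then be enough for both.

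**Precision at N = 328 for BCC prevalence π.** Sensitivity half-width = 1.96 √(0.95 × 0.05 / (328π)). Specificity half-width = 1.96 √(0.97 × 0.03 / (328(1 − π))). All values of π are assumptions.

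| BCC share | BCC / non-BCC (approx.) | Sensitivity | Specificity |
|---|---|---|---|
| 50% | 164 / 164 | ±3.3% | ±2.6% |
| 55% | 180 / 148 | ±3.2% | ±2.8% |
| 62% | 203 / 125 | ±3.0% | ±3.0% |
| 70% | 230 / 98 | ±2.8% | ±3.4% |
| 80% | 262 / 66 | ±2.6% | ±4.1% |
| 85% | 279 / 49 | ±2.6% | ±4.8% |

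Taken strictly, 203/125 is the only split with both half-widths at or below 3.00%: 202 BCC gives 3.006% for sensitivity, and 204 gives 3.003% for specificity. Rounded to one decimal, splits from 197 to 207 BCC (60% to 63%) keep both at 3.0%.

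**What the documents suggest about prevalence.** The only indirect evidence is the two-probe comparison cited in 'Background'. The odds of BCC there are PPV(1 − specificity) / [sensitivity(1 − PPV)].

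- Wide probe: 0.96 × 0.22 / (1.00 × 0.04) = 5.28, so 5.28 / 6.28 = 84% BCC.
- Handheld: 0.95 × 0.22 / (0.93 × 0.05) = 4.49, so 4.49 / 5.49 = 82% BCC.
- Cross-check from the handheld NPV: the odds of non-BCC are 0.70 × 0.07 / (0.78 × 0.30) = 0.209, so 1 / 1.209 = 83% BCC.

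Rounding of the published PPVs widens this to about 80% to 86%. It describes one other study and is not a planning value for this clinic. The description of lesions as equivocal could mean a lower share. At 82% to 84%, 328 patients would include about 52 to 59 non-BCC lesions, with specificity half-widths of about ±4.4% to ±4.6%.

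**Effect on the 94% rule.** This is the chance that the specificity lower limit reaches 94% at a true 97%, averaged over the binomial split of 328.

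| BCC share | Exact | Wilson | Wald |
|---|---|---|---|
| 62% | 24% | 24% | 53% |
| 70% | 17% | 17% | 47% |
| 82% | 6.5% | 5.6% | 45% |
| 84% | 2.1% | 1.6% | 43% |

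The low starting values at 62% come from the decision rule itself; only the fall down each column is due to prevalence. With exact or Wilson limits, 59 or fewer non-BCC lesions cannot pass even with no false positives (exact lower limit 93.94% at 59 of 59). The chance of having 59 or fewer is 53% at 82% BCC and 85% at 84%, but under 0.2% at 75% or below.

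**The case against.** The strongest reply is that 3% is a whole number. If a half-width need only round to 3% (below 3.5%), 328 is adequate for both measures from about 45% to 72% BCC. From 55% to 70% the worse of the two is only 3.2% to 3.4%. That is correct arithmetic, and it shows that the shortfall is modest in the middle of the range. It does not rescue the statement, because the plan calls 3% a maximum and sets its success limits exactly 3 points below the planned values.

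A second reply is that 125 and 203 are per-class counts by definition, and that open-ended accrual lets the team continue until both are reached. The plan does not say so. It fixes 328 as the recruitment target and ties continuation to reaching significance, not to 125 and 203.

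Third, the severe consequences depend on a BCC share above 80%, back-calculated from rounded figures in one cited study, and on an interval method that the plan leaves open. With Wald limits the chance of passing falls only from 53% to 43%. This stands as a limit on the size of the harm. The defect itself does not depend on direction: a departure either way breaks the claim for one measure.

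Finally, rewording does not raise the chance of meeting the 94% limit. That is true. What it corrects is a precision statement that the design does not support.

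**Conclusion.** The concern holds. The component figures and the addition are right, but the claim attached to the total is wrong as written: 328 patients give 3% for both measures only near 61.9% BCC, and no prevalence, quota or per-class target is stated anywhere. Over an assumed 50% to 85% BCC, the half-width runs from ±3.3% to ±2.6% for sensitivity and from ±2.6% to ±4.8% for specificity. The departure is small between about 55% and 70% BCC and material above about 80%.

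These half-widths rest on the plan's own normal-approximation formula and planned accuracies. The true prevalence, and so the direction of the miss, cannot be settled from the documents. The effect on the 94% rule depends further on the interval method: severe with exact or Wilson limits at a high BCC share, modest with Wald.

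**What to change.** Remove the claim of 3% for both measures, state BCC prevalence as an assumption, and report what 328 delivers over a range. Suggested wording:

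> The BCC share among biopsied lesions is not known in advance. Over an assumed 50% to 85% BCC, 328 patients give a 95% CI half-width of ±3.3% to ±2.6% for sensitivity and ±2.6% to ±4.8% for specificity; both are about 3% only near 62% BCC.

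This is enough to correct the point. It costs a rewrite of one paragraph and no extra patients, though the stated precision becomes less favourable for one of the two measures.

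If the sponsor wants to keep 3% for both, accrual could instead be defined by histology counts (203 BCC and 125 non-BCC), tracked by the co-ordinator, who is already unblinded. The plan says "Once the dataset is complete, assessment of the RCM images by the blinded investigators will take place", so stopping on these counts would not depend on the diagnostic readings; the check after 25 patients concerns image quality. The cost is a longer accrual that depends on case mix: 203 / 0.50 = 406 patients at 50% BCC, 125 / 0.30 = 417 at 70%, and roughly 690 to 790 at the 82% to 84% implied by the cited study (125 / 0.182 = 687; 125 / 0.159 = 786).

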Reflectance Confocal Microscopy (RCM) to diagnose basal cell carcinoma: HS-MAV-003

CHIEF INVESTIGATOR:

[name], MA (Oxon); MBBS; FRCP; PhD. Consultant Dermatologist,

Address and contact details:

Skin Care Network
[name]
[name]
[name]

Signature

Date 8-2-17

Sponsor:

Skin Care Network Barnet Ltd
[name]
[name]
[name]

Contents

Protocol Synopsis	3
Study Title:	4
Background.....	4
Aims.....	5
Study Design and Methods.....	5
Study Design	5
Study Hypothesis	5
Setting	5
Participants	5
Exclusion criteria	5
Informed Consent.....	5
Study Intervention	6
Statistics.....	7
Summary of statistical methods:.....	7
Sample size calculation.....	7
Data management and analysis	7
Ethical Issues	8
Amendments	8
Annual Progress Report	8
End of study report.....	8
Public disclosure and publication policy	8
Safety Considerations	9
Adverse and Serious Adverse Events (SAE).....	9
Follow-up of adverse events	9
Data Safety Monitoring Board.....	9
Sponsorship & Indemnity	9
Publication Policy	10
Data Safety Monitoring Board.....	10
References:	11
Appendix 1: Patient Information Sheet	Error! Bookmark not defined.
Appendix 2: Patient Consent Form	Error! Bookmark not defined.

Protocol Synopsis

Protocol ID	Version 0.5, 14 th February 2017
Protocol Title	HS-MAV-003
Development phase	II
Primary endpoint	Specificity & Sensitivity of RCM in diagnosing Basal Cell Carcinoma in non-pigmented lesions compared to standard histology
Secondary endpoint	Inter- & intra-observer agreement in assessing RCM images
Study design	This is a non-randomised, non-controlled, prospective observational study to look at the efficacy of in vivo RCM as a diagnostic tool in the diagnosis of BCC.
Key Inclusion Criteria	Patients 18 years or older with a suspected diagnosis of BCC
Key Exclusion Criteria	Recurrent or otherwise high-risk BCC Patient with basal cell naevus syndrome Patient treated with hedgehog inhibitor medication (vismodegib) Patient not suitable for diagnostic biopsy Location of lesion unsuitable, inaccessible or impractical for scanning with RCM as determined by investigator
Patient Accrual	328 patients over 18 months
Protocol follow-up procedure	None
Chief Investigator	[name]
Co-Investigators	[name], Dermatologie am Regierungsviertel Berlin.
Other key staff	[name] Consultant Dermatologist
Host Institution	Skin Care Network Barnet
Funding	None

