Should this diagnostic performance be shown to be replicable in an NHS setting, this would represent a significant opportunity to reduce waiting lists and save money, as patients with lower risk lesions could be diagnosed and treated during their first presentation to the skin cancer clinic. This would improve compliance

Recently, NICE guidance (Nov 2015) was issued regarding the use of RCM in the management of skin cancer [13]. They concluded the following:

“The VivaScope 1500 and 3000 imaging systems show promise but there is currently insufficient evidence to recommend their routine adoption in the NHS...”

“Further research...on using the VivaScope 1500 and 3000 imaging systems is recommended in the following areas:

...the impact on clinical workflows for melanoma and basal cell carcinoma assessment in secondary care settings.

...the number of confirmatory diagnostic biopsies needed for people with a clinical diagnosis of melanoma before definitive treatment is started."

If RCM is able to accurately diagnose basal cell carcinoma in the majority of lower risk patients then RCM would negate the requirement for diagnostic biopsy before listing patients for definitive treatment.

Aims

We propose to undertake a study to determine the diagnostic utility of using RCM for the diagnosis of Basal Cell Carcinoma (BCC) in a tertiary referral centre as outlined by the recent NICE report (Nov 2015). This will allow an assessment of the potential to avoid diagnostic biopsy within the treatment pathway.

Study Design and Methods

Study Design

This is an observational, non-randomised, non-controlled, prospective cohort study to look at the efficacy of *in vivo* RCM as a diagnostic tool in the diagnosis of BCC.

Study Hypothesis

The hypothesis of this study is that the use of RCM is would enable a reduction in the number of diagnostic biopsies taken before definitive treatment of BCC by at least 50%.

The secondary hypothesis is that the intra- & inter-observer agreement for interpreting the RCM images will have kappa scores 0.6 or greater (indicating good agreement).

Setting

Patients will be recruited from the outpatient clinic of Skin Care Network London.

Participants

The aim is to recruit 328 patients, who fit the following criteria:

1. Age 18 years or older.
2. Patient suspected of having a primary basal cell carcinoma that is a candidate for surgical treatment.
3. Patient willing and able to give informed consent.

Exclusion criteria

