Patients will be consented to having confocal microscopy performed of the target lesion before undergoing biopsy for histology. Acceptable biopsy methods will include punch, shave or excision biopsy with the intention of providing a diagnosis. These patients would be having photographs, including dermoscopic images, and a biopsy as part of their standard of care, therefore the only additional intervention is examination with the confocal microscope.

Confocal microscopy will be performed by a trained clinician, either a doctor or nurse specialist. Once the operator is satisfied that the images have been taken to a standard that will allow independent assessors to provide a diagnosis, they will be stored on a secure server and indexed anonymously with reference to the subject's assigned unique trial number. Imaging time is expected to last approximately 15-20 mins per patient. Similarly, the independent trial co-coordinator will archive the clinical images anonymously for future reference. In this way, data will be anonymised to allow blinding of the diagnosis with reference to the images during the analysis phase. The trial co-ordinator will be responsible for maintaining the database containing the patient and lesion information in addition to the images. The co-ordinator will be the only unblinded member of the investigatory team.

The images taken of the tumour by the confocal microscope will be anonymised. These images will then be examined by a different dermatologist who has undergone training in examining confocal images. The images will also be sent to a dermatologist in Berlin who is an expert in interpreting confocal microscopic images – both of these dermatologists will be blinded as to the patient's history and the results of the diagnostic biopsy. The clinicians interpreting the confocal microscope images will be asked to complete the following questions:

1. RCM description: features of BCC.
2. RCM diagnosis: BCC (Y/N); degree of certainty (0=low; 1=possible; 2=almost certain)

3. RCM quality of imaging: 0=low/don't feel confident; 1=acceptable/could be improved; 2=high quality (free text for images scoring 0)

The biopsies will undergo routine processing in our histopathology laboratory as normal and will be analysed by a pathologist who will be unaware of the findings on confocal microscopy.

Statistics

Summary of statistical methods:

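### The accrual sentence says recruitment continues until the study reaches significance; it should name the calculated numbers and rule out extension on results

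*Combined protocol and SAP*

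**What the plan says.** Data management and analysis, under Statistics, states: "The accrual period is estimated to be 12 months but will be continued until sufficient numbers are obtained for the study to reach significance". The sentence gives no number, maximum or schedule of analyses. It does not define significance, and the plan's success rules are confidence-limit criteria.

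Elsewhere the size is fixed:

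- Protocol Synopsis, Patient Accrual: "328 patients over 18 months".
- Participants: "The aim is to recruit 328 patients".
- Sample size calculation: "A total sample size of 328 will be required to test both a specificity of 97% and sensitivity of 95"%, being 125 for specificity plus 203 for sensitivity.

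Data management and analysis also sets an order. Data validation comes "once the recruitment target has been reached", the blinded readers assess the images when the dataset is complete, and the final analysis follows the end of recruitment. The only interim look, at 25 patients, concerns image quality.

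The success rules are in Summary of statistical methods. For specificity, "the lower limit of the 95% confidence interval must not be less than 94"%; for sensitivity, "the lower limit of the 95% confidence must not be less than 92"%. Neither is adjusted for repeated analysis, and the interval method is not named.

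**The concern.** A fixed target and recruitment until significance are different stopping rules, and the protocol contains both. Under the first, each lower-limit rule has a known chance of passing when true accuracy is only at the threshold. Under the second, that chance grows with each further test and the sentence sets no ceiling.

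What is at stake is the pass/fail claim that RCM matches biopsy, which the Background and Aims link to avoiding diagnostic biopsies. The accuracy estimate itself is hardly affected: under the schedules examined, the upward bias is at most 0.13 percentage points with exact or Wilson limits and 0.29 with Wald.

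**Working it through.** **1. The plan's own figure.** Inputs from Sample size calculation: expected values 97% and 95%, margin 3%, 95% interval. With n = 1.96² × p(1 − p) / d²:

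- specificity: 3.8415 × 0.97 × 0.03 / 0.0009 = 124.2, rounded up to 125;
- sensitivity: 3.8415 × 0.95 × 0.05 / 0.0009 = 202.7, rounded up to 203;
- total: 125 + 203 = 328.

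All three reproduce. This is a precision calculation, so 328 is not a number at which the study is expected to reach significance.

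**2. One analysis at the planned size.** For each interval, find the smallest number correct whose 95% lower limit is at least 94% (n = 125) or 92% (n = 203). Then take the binomial probability of reaching it, first with true accuracy at the threshold and then at the assumed value. One endpoint, one observer.

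| Rule | Limits | Passes from | Chance at threshold | Chance at assumed value |
|---|---|---|---|---|
| Specificity | Exact or Wilson | 123/125 | 1.8% | 27% |
| Specificity | Wald | 122/125 | 5.4% | 48% |
| Sensitivity | Exact or Wilson | 195/203 | 1.6% | 31% |
| Sensitivity | Wald | 193/203 | 6.2% | 56% |

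The chances of passing are low because each threshold is the assumed value minus the margin (97 − 3 = 94; 95 − 3 = 92), so the expected result sits at the edge of passing. The two measures use different lesions. For one observer, both therefore pass with probability 0.273 × 0.310 = 8% (exact or Wilson) or 0.481 × 0.564 = 27% (Wald).

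**3. If accrual were extended after a miss.** The protocol describes no such schedule, so these are assumptions. True accuracy is at the threshold. An exact binomial recursion removes passing paths at each look and sums their probability.

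- *One doubling, exact limits.* Specificity, 125 then 250: 2.86%. A single analysis at 250 gives 1.56%, so the extra look adds 2.86 − 1.56 = 1.30 points. Sensitivity, 203 then 406: 2.87%, against 1.77% for a single analysis at 406, so 2.87 − 1.77 = 1.10 points.
- *Re-tests every 25 lesions up to triple size (375 or 609), exact limits.* 5.9% for specificity and 6.8% for sensitivity, against at most 2.6% for a single analysis at any of those sizes.
- *Wald limits.* About 14–15% on the same triple-size schedule. Part of that belongs to the interval, which already gives 5.4% and 6.2% at one look.

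**4. What closing at 328 in total would secure.** Sensitivity needs BCC lesions and specificity needs non-BCC lesions, so both 3% margins hold only near 203/328 = 62% BCC. The documents give no expected proportion. Over an assumed range, with margin = 1.96 × √(p(1 − p)/n):

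| BCC | BCC / non-BCC lesions in 328 | Sensitivity margin | Specificity margin |
|---|---|---|---|
| 50% | 164 / 164 | 3.3% | 2.6% |
| 70% | 230 / 98 | 2.8% | 3.4% |
| 80% | 262 / 66 | 2.6% | 4.1% |
| 90% | 295 / 33 | 2.5% | 5.8% |

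**The case against.** A reader might infer that the trial plans to test repeatedly and stop when it succeeds. The documents do not support that. Stopping on the result needs accuracy figures during accrual, and the stated order leaves none, because images are read only when the dataset is complete. The section refers to a recruitment target, 328 appears in three other places, and the disputed sentence speaks of numbers just after numbers have been calculated. The natural reading is that recruitment runs past 12 months if the required numbers are not yet in. Under Study Intervention, "The co-ordinator will be the only unblinded member of the investigatory team". Changes affecting scientific value must be notified as substantial amendments, and the publication policy commits to publishing negative results.

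Most of this stands. Loose wording is the likelier explanation, the harm is conditional, and the re-test schedules have no basis in the text. The low chance of passing concerns power; it shows when the sentence might be invoked, not that it would be.

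What remains is that no section says accrual closes at the calculated numbers, or that it may not be re-opened once the limits are known. Blinding protects the image readings, not a decision taken after analysis. The amendment procedure may not be triggered, because the present sentence arguably already permits an extension. A promise to publish negative results does not say when a result is final.

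A further objection also stands: simply naming 328 would be an incomplete repair, since the total alone does not secure the two class sizes.

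**Conclusion.** The sentence is wrong as written and should be corrected. It contradicts the fixed 328 and the section's own sequence, and read literally it has no maximum. If that sequence is kept with one analysis at the planned size, there is no inflation. If accrual were extended after a missed limit, the false-pass chance per rule with exact limits would go from 1.6–1.8% to about 2.9% (one doubling) or about 6–7% (every 25 lesions to triple size). Those figures assume true accuracy at the threshold, one endpoint, one observer and schedules that the protocol does not contain. They do not show that the error rate of the planned analysis is inflated. Severity: a minor to moderate wording correction.

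**What to change.** Replace the sentence with:

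> The accrual period is estimated at [one reconciled duration]. Accrual continues until the numbers in the sample size calculation are reached (203 histologically confirmed BCC lesions and 125 non-BCC lesions, 328 in total if the case mix allows). Any extension is based only on these histology counts. No sensitivity, specificity or kappa is calculated before accrual closes, and accrual is not extended or re-opened on the basis of those results.

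The duration must be reconciled because the synopsis gives 18 months and Data management and analysis gives 12. The unblinded co-ordinator can track the histology counts without any RCM reading being made.

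If the sponsor prefers to close at 328 in total, keep the ban on result-based extension and state that the 3% margin holds for both measures only at about 62% BCC.

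Cost: a short edit and no new procedures. The sponsor gives up the option to extend after seeing results. With class counts, accrual may exceed 328. The total needed is the larger of 203/π and 125/(1 − π), where π is the BCC proportion: 406 at 50%, 417 at 70%, 625 at 80% and 1,250 at 90%, all assumed values. The sponsor should weigh that before choosing between the two versions.
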